3.5.5 Statistical Methods

3.5.5.1 Immunogenicity Analyses

The primary hypotheses of non-inferiority of GMTs for the oncogenic HPV types 16, 18, 31, 33, 45, 52, and 58 will be addressed by 7 one-sided tests of non-inferiority (one corresponding to each HPV type) conducted at Type I error $\alpha=0.025$ (1-sided). For each HPV type, the hypotheses to be tested are:

$$H_0: \text{GMT}_{\text{AW}}/\text{GMT}_{\text{YAW}} \leq 0.50$$

$$\text{Versus} H_1: \text{GMT}_{\text{AW}}/\text{GMT}_{\text{YAW}} > 0.50$$

where GMT_{AW} represents the GMTs at Month 7 in 27- to 45-year-old subjects and GMT_{YAW} represents the GMTs at Month 7 in 16- to 26-year-old subjects. The hypothesis testing will be conducted using an ANOVA model with a response of log individual titres and a fixed effect for age group. The statistical criterion for non-inferiority requires that the lower bound of two-sided 95% confidence interval (CI) of GMT ratio (27- to 45-year-old subjects versus 16- to 26-year-old subjects) being greater than 0.50.

It is assumed that the true GMT ratio AW/YAW is 0.7 which is based on the results from V501 Protocol 019 where GMTs were observed to decrease with age at vaccination. The proposed approach (using a non-inferiority margin of 2.0) is appropriate to estimate the GMT ratio and corresponding 95% CIs, and assess any negative trend in immunogenicity with GARDASIL®9 in AW compared to YAW. Moreover, the scientific merit of a non-inferior margin of 1.5 would be limited as there is currently no known minimum immunologic correlate for HPV vaccine efficacy, due to high efficacy of GARDASIL®9; it is not expected to add further clinical significance to the results. A study powered for a more stringent non-inferiority margin would require a substantial increase in sample size which was not deemed necessary for the purpose of this study, based on the immunogenicity data available when this study was designed.

The secondary hypotheses of acceptability of the anti-HPV 16, 18, 31, 33, 45, 52 and 58 seroconversion rates in the 27- to 45-year-old women group will be tested based on the 95% CIs for the single group proportion calculated using the exact binomial method (Clopper-Pearson method) for single proportions. For each HPV type, the statistical criterion for acceptability requires that the lower bound of the 95% CIs of the seroconversion rate for each of the antigens is greater than 90%.

V503-004-02

15-Mar-2017

Primary and secondary endpoints (including anti-HPV 6, 11, 16, 18, 31, 33, 45, 52, and 58 GMTs and seroconversion rates at 4 weeks after Dose 3) will be summarized within each age group and enrolment strata (16- to 20-year-olds and 21- to 26-year-olds for YAW and 27- to 36-year-olds and 37- to 45-year-olds for AW [Section 2.4.1]) for all subjects in the PPI analysis populations. Furthermore, in order to assess the sensitivity of the results, these analyses will be repeated on the ANSS analysis populations.

In calculations of GMTs by HPV type, cLIA titres reported as less than the Lower Limit of Quantification (LLOQ) of the relevant HPV type will be replaced by the half of the LLOQ in the numerical computation of GMT. No search for outliers will be performed.

In addition, reverse cumulative distribution curves will be provided for graphical comparisons of distributions of HPV titres by age groups.

3.5.5.2 Statistical Methods for Safety Analyses

Safety and tolerability will be assessed by statistical and clinical review of all safety data collected throughout the study. Summaries will be provided for each age group. Statistical analyses of AEs will follow the 3-tiered analysis approach commonly used by the Sponsor when conducting safety assessments, as outlined in Section 2.7.2.

Regardless of incidence, all AEs will be summarized as frequencies and percentages by each age group, by vaccination visit, and across all vaccination visits.

Specific AEs for which summaries will be provided are identified in [Table 7](#).

Incidence is defined as (number of subjects with the indicated endpoint divided by the total number of subjects with follow-up over the relevant period) $\times 100\%$.

Confidence intervals (95%) and 2-sided p-values will be provided without adjusting for multiplicity.

The method of Miettinen and Nurminen [20] will be used for all comparisons of groups.

Risk differences, CIs, and p-values will be computed across all sites combined (i.e., no stratification by study sites will be performed).

Treatment administration data will be summarized for each age group including number of vaccine injections received. Imputation methods will not be used to replace missing safety data.

Table 7 Analysis Strategy for Safety Parameters

Adverse Event Endpoint	Follow-Up Period			Summaries/Analyses		
	After Any Vaccination Visit		Any Time During Study	Incidence	Risk Difference and 95% CI (b)	p-Value
	Day 1 to Day 5 (a)	Day 1 to Day 15 (a)				
Clinical AEs						
• Any AE		•		•		
• Deaths			•	•		
Injection-site adverse reactions (c)						
• Injection-site pain/tenderness, swelling, and redness	•			•	•	•
• Other injection-site adverse reactions	•			•	• (d)	
• Severe injection-site adverse reactions	•			•	•	
• Number (%) of subjects by maximum intensity rating, over all injection-site adverse reactions	•			•		
• Number (%) of subjects by maximum intensity rating, within each of the categories of injection-site adverse reactions	•			•		
Systemic AEs						
• Systemic AEs		•		•	• (e)	
• Number (%) of subjects by maximum intensity rating, over all systemic AEs		•		•		
Temperatures						
• Elevated temperatures (f)	•			•	•	•
• Maximum temperatures (g)	•			•		
AEs of Special Interest						
• Serious AEs		•		•	•	
• Serious VR AEs			•	•	•	
• New medical conditions			•	•		
(a) The day of vaccination is counted as Day 1.						
(b) Defined as the difference in incidence between the comparison groups.						
(c) For the injection-site redness and swelling 0 to 2.5 cm (0 to 1 inch) will be categorized as mild, >2.5 to 5 cm (>1 inch to 2 inches) will be categorized as moderate, and >5 cm (>2 inches) will be categorized as severe.						
(d) Only for injection-site adverse reactions occurring in $\geq 1\%$ of subjects in either group.						
(e) Only for systemic AEs occurring in $\geq 1\%$ of subjects in either group.						
(f) Defined as maximum (over the follow-up period) temperature $\geq 37.8^{\circ}\text{C}$ ($\geq 100^{\circ}\text{F}$, oral equivalent).						
(g) Distribution of maximum temperatures over the relevant follow-up period.						
AEs, adverse events; VR, vaccine-related.						

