2.1.2 Secondary Objectives

The secondary objectives are:

To evaluate the safety/tolerability of GARDASIL®9 in 27- to 45-year-old women compared with 16- to 26-year-old women;

To demonstrate that GARDASIL®9 is immunogenic with respect to HPV types 16, 18, 31, 33, 45, 52, and 58 in 27- to 45-year-old women;

To summarize humoral immune responses (including anti-HPV 6, 11, 16, 18, 31, 33, 45, 52, and 58 GMTs and seroconversion rates at Day 1 and 4 weeks after Dose 3) in 16- to 26-year-old and 27- to 45-year-old women who received GARDASIL®9.

Hypothesis: GARDASIL®9 generates anti-HPV 16, 18, 31, 33, 45, 52 and 58 seroconversion rates 4 weeks after Dose 3 that are acceptable in 27- to 45-year-old women who are seronegative at Day 1 to the relevant HPV type(s). (Seroconversion is defined as changing serostatus from seronegative at Day 1 to seropositive by 4 weeks after Dose 3) (The seroconversion rate for each of the HPV types 16, 18, 31, 33, 45, 52, and 58 will be tested separately. Acceptability is defined as the lower bound of the two-sided 95% CI for the seroconversion rate being greater than 90%).

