2.7.2 Safety Analyses

All subjects who received at least 1 dose of GARDASIL®9 and have safety follow-up data will be included in the analysis of safety. Statistical analyses of AEs will follow the 3-tiered analysis approach commonly used by the Sponsor/Vaccine Manufacturer when conducting safety assessments.

Tier 1 analysis compares between group difference by providing incidence summaries by each group, computing (incidence) risk differences and 95% CIs of risk differences between groups and computing p-values corresponding to tests of significance of the risk differences. P-values and 95% CIs for between-age-group differences in the percentage of subjects with events will be calculated using the Miettinen and Nurminen [20] method.

Tier-1 AEs in this study include:

- injection-site adverse reactions prompted for on the eVRC occurring Day 1 to Day 5 following any vaccination, and
- elevated temperatures ($\geq 37.8^{\circ}\text{C}$ or 100.0°F) from Day 1 to Day 5 following any vaccination.

Tier 2 analysis follows the Tier 1 analysis approach, except p-values are not computed.

Tier-2 AE summaries include:

- systemic AEs within 14 days following any vaccination occurring in $\geq 1\%$ of subjects in any group,
- injection-site adverse reactions not prompted for on the eVRC occurring Day 1 to Day 5 following any vaccination in $\geq 1\%$ of subjects in any group,
- SAEs occurring within 14 days (Day 1 to Day 15) following any vaccination,
- serious vaccine-related AEs observed at any time during the study, and
- severe injection-site adverse reactions Day 1 to Day 5 following any vaccination visit.

Tier-3 AEs include summaries (counts and percentages) by each age-group for any other AEs, including all injection-site adverse reactions occurring from Day 1 to Day 5 following each vaccination visit, all systemic AEs occurring within 14 days (Day 1 to Day 15) of each vaccination visit, and all SAEs occurring during the study and not included in the Tier-2 analysis.

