3.4.2.3 Immediate Reporting of Adverse Events to the Sponsor

3.4.2.3.1 Serious Adverse Events

A serious adverse event is any adverse event occurring at any dose or during any use of Sponsor's product that:

- Results in death;
- Is life threatening;
- Results in persistent or significant disability/incapacity;
- Results in or prolongs an existing inpatient hospitalization;
- Is a congenital anomaly/birth defect;
- Is a cancer;
- Is associated with an overdose;
- Is another important medical event

Refer to [Table 4](#) for additional details regarding each of the above criteria.

Any serious adverse event, or follow up to a serious adverse event, including death due to any cause, that occurs to any subject from the time the consent is signed through 1 month following the last vaccination, whether or not related to the Sponsor's product, must be reported within 24 hours to the Sponsor either by electronic media or paper. Sponsor Contact information can be found in the Investigator Trial File Binder.

Additionally, any serious adverse event brought to the attention of an investigator who is a qualified physician at any time outside of the time period specified in the previous paragraph also must be reported immediately to the Sponsor if the event is either:

- A death that resulted in the subject discontinuing the trial
 - or
- A serious adverse event that is considered by an investigator who is a qualified physician to be vaccine related.

All subjects with serious adverse events must be followed up for outcome.

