3.5.3.2 Safety

Safety assessment will focus on injection-site adverse reactions and elevated temperatures Day 1 to Day 5 post-vaccination and systemic AEs Day 1 to Day 15 post-vaccination, reported on the electronic VRC. In addition, SAEs and pregnancy will be collected from the time the ICF is signed through 1 month following the last vaccination.

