The number and percentage of subjects with prior medications or vaccinations prior to each study vaccination will be summarized for each age group. The relevant pre-injection day

ranges for summarization will be 3 days for medications, 14 days for non-live virus vaccines, and 21 days for live virus vaccines.

Similarly, the number and percentage of subjects with concomitant medications or vaccinations within 15 days (Day 1 to Day 15) following any study vaccination will be summarized for each age group. The number of subjects with “Special Medications” (corticosteroids, immunosuppressives, immune globulins, and blood products [Section3.2.4]) will be summarized for each age group throughout the study period.

New Medical Conditions: New medical conditions occurring during the study (i.e., incident medical conditions occurring outside of a Day 1 to Day 15 period post-vaccination and not considered SAEs) will be summarized for each age group.

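### Does the safety analysis need a full-period all-cause SAE row in Table 7, which compares all-cause SAEs only on Day 1 to Day 15 after each dose?

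*Combined protocol and SAP*

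**What the plan says.** One secondary objective (Section 2.1.2) is "To evaluate the safety/tolerability of GARDASIL®9 in 27- to 45-year-old women compared with 16- to 26-year-old women". Section 3.4.2.3.1 requires SAEs to be reported "from the time the consent is signed through 1 month following the last vaccination, whether or not related to the Sponsor's product", and Section 3.5.3.2 repeats the period: "SAEs and pregnancy will be collected from the time the ICF is signed through 1 month following the last vaccination".

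The analysis is described in two places. Section 3.5.5.2 says "Specific AEs for which summaries will be provided are identified in" Table 7, and follows the three tiers of Section 2.7.2 by reference. Tier 2 (incidence, risk difference, 95% CI, no p-value) includes "SAEs occurring within 14 days (Day 1 to Day 15) following any vaccination" and, separately, vaccine-related SAEs at any time. Tier 3 (counts and percentages by age group) includes "all SAEs occurring during the study and not included in the Tier-2 analysis". Table 7 carries the two Tier 2 items with the same periods, plus any-time rows for deaths and for new medical conditions, both with incidence only. Section 3.5.5.3 defines the latter as "incident medical conditions occurring outside of a Day 1 to Day 15 period post-vaccination and not considered SAEs". Section 3.5.5.2 also states that, whatever their incidence, "all AEs will be summarized as frequencies and percentages by each age group, by vaccination visit, and across all vaccination visits".

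**The concern.** Table 7 has no row for any SAE over the whole follow-up. The only all-cause SAE comparison is confined to the post-dose windows, although the data run for about seven months. The table also looks lopsided: a non-serious condition arising outside the windows has a named any-time row, while a serious, non-fatal, vaccine-unrelated one on the same day has none and reaches the report only through Tier 3.

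Tier 3 is most naturally read as what is left after Tier 2. A woman with one SAE inside a window and another outside could then appear in both tabulations, and the two percentages would not strictly add up to the proportion of women with any SAE. If late serious events went unreported or could not be interpreted, the comparative safety objective would be poorly served. The primary immunogenicity conclusion is not touched in any case.

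**Working it through.** **Share of follow-up days.** Inputs: three doses at Day 1, Month 2 and Month 6; a month is 30 days (Section 1.7, footnote a); SAEs are followed for 30 days after the last dose (Section 1.7, footnote i); the day of vaccination is Day 1 (Table 7, note a).

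- Follow-up: 6 × 30 + 30 = 210 days = 7.0 months, which reproduces the approximate seven months in Section 1.4. Counting the first day as Day 1 gives 211.
- Compared days: 3 × 15 = 45. The windows cannot overlap within the visit windows, since Dose 2 falls no earlier than 60 − 21 = 39 days after Dose 1, and Dose 3 (earliest 180 − 28 = 152) at least 152 − 81 = 71 days after Dose 2.
- Share: 45/211 = 21.3%. With Dose 3 from 152 to 208 days after Dose 1, the period is 183 to 239 days and the share 24.6% to 18.8%.

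This is a share of days. It is not a share of events.

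**Where each event is reported.**

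| Event | On Day 1–15 after a dose | On other days |
|---|---|---|
| Vaccine-related SAE | Incidence, risk difference, CI | Incidence, risk difference, CI (any-time row) |
| Death | SAE row with risk difference and CI; deaths row | Deaths row, incidence |
| Other SAE | Incidence, risk difference, CI | Tier 3, counts and percentages |
| Non-serious new condition | Recorded as an AE | New-conditions row, incidence only |

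No cell is empty. Late unrelated SAEs and late non-serious conditions get the same kind of output, a count and percentage by age group without a risk difference. The difference is only that Table 7 prints one of the two.

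**How far the two tabulations could mislead if added.** The documents give no SAE rate, so assume 1% to 3% of 600 women per group, spread evenly over the days.

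- 3%: 18 women. Inside the windows 18 × 45/211 = 3.84; outside 18 − 3.84 = 14.16.
- Taking these as the two tabulated counts, the number with any SAE lies between 14.16 (complete overlap, 2.4%) and 18 (no overlap, 3.0%).
- With independent overlap, 3.84 × 14.16/600 = 0.09 woman is counted twice.
- 1%: 6 women, 1.28 inside and 4.72 outside; independent overlap 1.28 × 4.72/600 = 0.01 woman.

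The sum misleads only if SAEs cluster strongly in the same women.

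**What a full-period risk difference would show.** Miettinen–Nurminen 95% CIs with 600 per group and equal rates have half-widths of about 1.3, 1.7 and 2.0 percentage points at 1%, 2% and 3%. An assumed 20 versus 15 women gives +0.8 points (−1.1 to +2.9).

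**The case for a change.** The strongest case for a change is that the percentage of women with any SAE during follow-up is a basic safety summary, that comparing safety between the age groups is a stated objective, and that no named output gives this figure. The any-time comparison of vaccine-related SAEs depends on causality judged by investigators in an open-label study, whereas an all-cause row would not. The promise to summarize all AEs across visits does not settle the matter, because it names neither SAEs nor a period, and non-serious AEs are collected only through 14 days after each dose. One extra row would cost almost nothing.

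The factual part stands: the row is not named, and the sentence on all AEs is ambiguous. The rest carries less weight. An SAE judged unrelated stays visible by age group in Tier 3, so a causality judgement cannot hide it. Every woman receives the same vaccine and the groups are defined by age, so a difference in late, unrelated SAEs would largely reflect age. Fetal losses are reported as SAEs (Section 3.4.2.2), so an all-cause figure would also depend on how many women conceive. Low cost makes the row reasonable to add, but it does not make its absence a fault.

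**Conclusion.** No change is needed. The comparison concentrates on the days after each dose and on vaccine-related SAEs throughout, and leaves other late SAEs to description. That is a coherent choice, consistent between Section 2.7.2 and Table 7, and it loses no SAE. The gap is one combined descriptive percentage and its interval. An analyst can produce both from data already collected, and Section 3.5 already provides for listing changes to non-confirmatory analyses in the study report.

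The 21% describes days for a woman dosed on schedule; pregnancy delays or early discontinuation would alter it. The overlap figures (0.01 to 0.09 woman per group) rest on assumed SAE risks of 1% to 3%, even timing and independent overlap, and strong clustering would make them larger. At those risks the added risk difference would have an interval of about ±1.3 to ±2.0 points and would not resolve small differences between the age groups.

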3.5.5.3 Summaries of Baseline Characteristics, Demographics, and Other Analyses

Baseline characteristics and demographic variables will be summarized by age groups using descriptive statistics or categorical tables on all subjects enrolled in the study and on all PPI-eligible subjects (i.e., subjects belonging to at least one PPI analysis populations). No formal statistical testing of differences between age groups with respect to these characteristics will be performed.

Quantitative variables (except antibody titres) will be displayed using descriptive statistics by way of sample size, mean, standard deviation, median, minimum, and maximum. Antibody titres will be displayed using descriptive statistics by way of sample size, GMTs, and two-sided 95% CIs.

Categorical variables will be displayed using descriptive statistics by way of sample size, count by category, and proportion by category. Missing data will be counted but not included in the calculation of proportions.

Subject Accounting

The number and percentage of subjects screened (ICF signed), enrolled (allocation number assigned), vaccinated (at least once and at each vaccination time point), discontinued, and the primary reason for discontinuation will be displayed by age group. Reasons for subjects excluded from the PPI analysis populations will be summarized and displayed in subject accounting tables. A summary of subjects screened/vaccinated by country/site will be provided.

Subject Characteristics

Demographic variables and other baseline characteristics such as age, vital signs (height, weight, and oral temperature), and country will be summarized by strata and age group.

Baseline HPV Status

A serum sample will be collected from all subjects at the Day 1 visit for the purpose of assessing baseline HPV serostatus to the 9vHPVvaccine HPV types (HPV 6, 11, 16, 18, 31, 33, 45, 52, and 58). A subject will be considered seropositive to a given HPV type at Day 1 if the subject's anti-HPV titre is greater than or equal to the corresponding serostatus cutoff for that HPV type or seronegative to a given HPV type at Day 1 if the subject's anti-HPV titre is less than the corresponding serostatus cutoff for that HPV type. For each HPV type, the proportions of subjects who are seronegative or seropositive will be summarized by strata and age group.

Prior and Concomitant Medications

The number and percentage of subjects with prior medications or vaccinations prior to each study vaccination will be summarized for each age group. The relevant pre-injection day

ranges for summarization will be 3 days for medications, 14 days for non-live virus vaccines, and 21 days for live virus vaccines.

Similarly, the number and percentage of subjects with concomitant medications or vaccinations within 15 days (Day 1 to Day 15) following any study vaccination will be summarized for each age group. The number of subjects with “Special Medications” (corticosteroids, immunosuppressives, immune globulins, and blood products [Section3.2.4]) will be summarized for each age group throughout the study period.

New Medical Conditions: New medical conditions occurring during the study (i.e., incident medical conditions occurring outside of a Day 1 to Day 15 period post-vaccination and not considered SAEs) will be summarized for each age group.

3.5.6 Multiplicity

For the primary hypotheses, success requires that non-inferiority be established for all oncogenic HPV types (i.e., 16, 18, 31, 33, 45, 52, and 58); thus, no multiplicity adjustment is necessary for this study.

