2.7 Data Analysis Summary

2.7.1 Immunogenicity Analyses

The primary analyses of immunogenicity will be conducted in the Per Protocol Immunogenicity (PPI) population as defined in Section 3.5.4.1.

The primary hypotheses of non-inferiority of GMTs for HPV oncogenic types 16, 18, 31, 33, 45, 52, and 58 will be based on one-sided tests of non-inferiority comparing Month 7 GMTs for each component. Analysis of variance (ANOVA) models (one per HPV oncogenic type) with a response of log individual titres and a fixed effect for age group will be used. The hypotheses to be tested are: $H_0: \text{GMT}_{\text{AW}}/\text{GMT}_{\text{YAW}} \leq 0.50$ versus $H_1: \text{GMT}_{\text{AW}}/\text{GMT}_{\text{YAW}} > 0.50$, where GMT_{AW} represents the GMTs in 27- to 45-year-old subjects and GMT_{YAW} represents the GMTs in 16- to 26-year-old subjects. Each hypothesis will be tested at $\alpha=0.025$ level (one-sided). The statistical criterion for non-inferiority in these tests corresponds to the lower bound of the two-sided 95% CI for the geometrical mean ratio of 27- to 45-year-old subjects versus 16- to 26-year-old subjects being greater than 0.50. Success of the study will be declared if non-inferiority can be confirmed for all HPV oncogenic types. Therefore, no adjustment for multiplicity is required.

For this study on women 16- to 45-years of age, the rate of exclusion from the PPI analysis populations is expected to range from 25% to 35% of enrolled subjects mainly due to HPV seropositivity at baseline and possibly protocol deviations that could potentially interfere with immune response to vaccination of GARDASIL®9. The expected GMT ratio AW/YAW is 0.7, reflecting the fact that the immunogenicity of any HPV vaccine decreases with the increasing age of the subjects, and the variability (standard deviation) of each serotype on the natural log scale is estimated to be 1.2. If 1,200 subjects are enrolled in the study in a 1:1 fashion with regards to the 2 age groups, the evaluable population will range from 780 to 900 subjects. If the exclusion rate from PPI analysis population is 35% for 1 HPV type and 25% for the 6 others, this study will have over 90% power to rule out a 2-fold decrease in GMT for the 7 oncogenic HPV types (Types 16, 18, 31, 33, 45, 52, and 58).

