The secondary hypotheses of acceptability of the anti-HPV 16, 18, 31, 33, 45, 52 and 58 seroconversion rates in the 27- to 45-year-old women group will be tested based on the 95% CIs for the single group proportion calculated using the exact binomial method (Clopper-Pearson method) for single proportions. For each HPV type, the statistical criterion for acceptability requires that the lower bound of the 95% CIs of the seroconversion rate for each of the antigens is greater than 90%.

Assuming a true seroconversion rate to each HPV type >98% and a percentage of subjects excluded from the PPI analysis population <35% for HPV 16 and <25% for HPV 18, 31, 33, 45, 52 and 58, the power of the secondary hypothesis testing is >99% using a Type I error $\alpha=0.025$ (one-sided).

Another secondary objective is to summarize HPV antibody responses (including anti-HPV 6, 11, 16, 18, 31, 33, 45, 52, and 58 GMTs and seroconversion rates at Day 1 and 4 weeks after Dose 3) in 16- to 26-year-old and 27- to 45-year-old women who received GARDASIL®9. In

addition, exploratory analyses will be conducted to provide HPV antibody responses by age strata (i.e., 16- to 20-year-olds and 21- to 26-year-olds for YAW and 27- to 36-year-olds and 37- to 45-year-olds for AW).

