3.5.2 Hypothesis/Estimation

Objectives and hypotheses of the study are stated in Section 2.1.

The study will be considered a success if the non-inferiority criteria for GMTs are met for HPV types 16, 18, 31, 33, 45, 52, and 58 for the comparisons between 27- to 45-year-old women versus 16- to 26-year-old women that received GARDASIL®9.

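### Does the no-adjustment statement in Section 3.5.6 leave the seven secondary seroconversion tests without error control?

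*Combined protocol and SAP*

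**What the plan says.** Section 3.5.6 is a single sentence. Its premise is "For the primary hypotheses, success requires that non-inferiority be established for all oncogenic HPV types" and its conclusion is "thus, no multiplicity adjustment is necessary for this study". Section 2.7.1 gives the same argument in its paragraph on the primary tests: "Success of the study will be declared if non-inferiority can be confirmed for all HPV oncogenic types". Section 3.5.2 ties study success to the same tests: "The study will be considered a success if the non-inferiority criteria for GMTs are met".

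The secondary seroconversion objective is also a formal hypothesis. Section 2.1.2 puts all seven oncogenic types into one hypothesis for women aged 27 to 45 and adds: "The seroconversion rate for each of the HPV types 16, 18, 31, 33, 45, 52, and 58 will be tested separately". Section 3.5.5.1 uses Clopper-Pearson intervals and, type by type, requires that "the lower bound of the 95% CIs of the seroconversion rate for each of the antigens is greater than 90" per cent. Sections 2.7.1 and 3.5.7.1 add a one-sided Type I error of 0.025 and a power statement: "the power of the secondary hypothesis testing is >99" per cent.

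No section states an all-seven rule, a testing order, an alpha split or a gate on the primary for these tests.

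**The concern.** The reason in Section 3.5.6 is an intersection-union argument. If every component must pass before anything is claimed, each can be tested at the full level. That argument is made only for the GMT tests, yet the conclusion is worded for the whole study. The seroconversion tests have a threshold, an alpha and a power, so they cannot be set aside as descriptive.

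For the primary, the all-types rule is spelled out in Sections 2.7.1, 3.5.2 and 3.5.6. For the secondary it is not. A reader could take the criterion type by type, claim acceptability for whichever types pass, and cite Section 3.5.6 as the reason for not adjusting. Seven unadjusted one-sided 0.025 tests would then not hold the error of the secondary family at 2.5%.

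**Working it through.** **Inputs.** From Section 3.5.7.1: 600 women per age group; exclusion of 35% for one type (HPV 16 in the secondary power statement) and 25% for the other six; assumed true seroconversion above 98%; one-sided alpha 0.025. From Section 3.5.5.1: exact lower 95% bound above 90%. Evaluable women aged 27 to 45: 600 × 0.65 = 390 for one type and 600 × 0.75 = 450 for six.

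**Passing counts.** The lower bound for x of n is the 0.025 quantile of Beta(x, n − x + 1).
- n = 390: 363 gives 0.9009 (pass); 362 gives 0.8979 (fail).
- n = 450: 418 gives 0.9011 (pass); 417 gives 0.8986 (fail).

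**The plan's own figure.** At a true rate of 98%, P(X ≥ 363 of 390) and P(X ≥ 418 of 450) both exceed 0.9999. With all seven required and independent types, the product also exceeds 0.9999. The stated power above 99% is reproduced under either reading, so it does not show which rule was meant.

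**Size of one test at a true rate of exactly 90%.** a = 0.0220 (n = 390) and b = 0.0210 (n = 450). Because the stated exclusions are upper limits, n may be larger. For n from 390 to 600 the exact size ranges from 1.6% to 2.5%.

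**All-seven reading.** A false claim requires a type with a true rate at or below 90% to pass, so the error cannot exceed that type's own size: at most 2.5%, whatever the correlation. Joint power under independence:

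| True rate, all types | Joint power |
|---|---|
| 98% | above 99.99% |
| 97% | above 99.99% |
| 96% | 0.9976 × 0.99926⁶ = 99.3% |

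**Type-by-type reading.** Under independence, P(at least one false claim) = 1 − (1 − a)(1 − b)⁶.

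| True rate, all seven types | a | b | P(at least one) |
|---|---|---|---|
| 90% | 0.0220 | 0.0210 | 13.9% |
| 89.5% | 0.0101 | 0.0090 | 6.2% |
| 89% | 0.0043 | 0.0035 | 2.5% |
| 88% | 0.0007 | 0.0005 | 0.3% |

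At 90% the bound without independence is a + 6b = 14.8%. An equicorrelated normal model with the same exact sizes gives 11.8%, 9.9% and 7.7% at correlations of 0.3, 0.5 and 0.7. The documents give no correlation, so these values are assumptions. If only one type is at 90% and the rest are well above, the figure is 2.1% to 2.2%.

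**Which reading the text supports.**
- Section 2.1.2 states one objective and one hypothesis naming all seven types.
- The criterion in Section 3.5.5.1 runs over every antigen.
- The power statement is a single figure for the secondary testing, with exclusion rates given for all seven types.
- Separate testing does not imply separate claims. Section 2.1.1 also analyses the primary GMT ratios separately, and all seven must still pass.

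**The case for a change.** The strongest case for a change is that the sponsor wrote the all-types rule down for the primary, where the criterion is likewise given per type, and wrote no such sentence for the secondary. Two sentences in Section 3.5.6 would remove the choice between readings before results are known, at no cost in subjects or in the stated power. Where the plan leaves error uncontrolled on purpose, for safety in Section 3.5.5.2, it says so.

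The textual part stands: the conclusion in Section 3.5.6 is wider than its premise, and the secondary rule is implied, not stated. The rest does not show that the plan goes wrong. The added sentences would record the rule that the text already suggests. If types were claimed singly, each HPV type has its own analysis population and criterion (Sections 3.5.4.1 and 3.5.5.1), and statisticians reasonably differ on whether such secondary statements need family-wise control. The plan does not commit itself to that control.

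The 13.9% also needs all seven true rates to sit on the threshold. Section 1.3 reports 99.6% to 100% seropositive by Month 7 in the groups tested so far. Those groups did not include women over 26, so the figure supports the assumption above 98% only indirectly.

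**Conclusion.** No change to the plan is needed. Section 3.5.6 is worded loosely, and the secondary decision rule is a gap that analysts would fill with the all-seven reading. On that reading no adjustment is needed, error is at most 2.5%, and joint power exceeds 99.99% at 98% seroconversion. The primary decision, its Type I error and the stated powers are the same under either reading.

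Type-by-type claims could raise the secondary family's error to 13.9% under independence (14.8% as a bound), but only with all seven true rates at exactly 90%. That is far from the assumed rates above 98%. At those rates every type would be expected to pass under either reading, so the secondary conclusion would be the same.

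These figures rest on 390 and 450 evaluable women and on the stated exclusion rates. The correlated cases rest on assumed correlations.
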